6.4 Adverse Event Updates/IND Safety Reports

Celgene shall notify the Investigator via an IND Safety Report of the following information:

- Any AE that is possibly, probably or definitely associated with the use of drug in this study or in other studies that is both serious and unexpected.
- Any finding from tests in laboratory animals that suggests a significant risk for human subjects including reports of mutagenicity, teratogenicity, or carcinogenicity.

The Investigator shall notify the University of Pennsylvania IRB promptly of any new serious and unexpected AE(s) or significant risks to subjects that meet the local reporting policy.

The Investigator must keep copies of all AE information, including correspondence with Celgene and the IRB on file (see Section 11.4 for records retention information).

7 Response Assessment

Baseline lesion assessments must occur within ≤ 28 days of protocol therapy initiation or as indicated in Section 2, Schedule of Study Assessments.

Efficacy assessments are scheduled to occur within 28 days prior to starting lenalidomide therapy, every three cycles during the first year, and every four cycles during the second year of study participation. Clinical assessments, including laboratory studies and physical exams, will occur monthly throughout study participation. Follow-up contact with the subjects should occur at a minimum of 3 months during the three years after finishing maintenance phase and annually after that. The frequency of follow-up imaging after completing 24 cycles of lenalidomide maintenance will be at discretion of the treating physician.

8 Protocol Amendments and Deviations

8.1 Protocol Amendments

Any amendment to this protocol must be agreed to by the Principal Investigator and reviewed by Celgene. Amendments should only be submitted to IRB/CTSRMC after consideration of Celgene review. Written verification of IRB/CTSRMC approval will be obtained before any amendment is implemented.

8.2 Protocol Deviations

Reportable Events:

An one-time accidental or unintentional deviation from the approved protocol, identified retrospectively, that in the opinion of the investigator or as defined by the protocol, placed one or more participants at increased risk, compromises the rights or welfare of subjects, and/or disrupts the study design, is considered a reportable event and must be reported to the Study Principal Investigator, Study Medical Monitor, IRB, and ACC DSMC within 10 working days of notification. Principal Investigator and Medical Monitor approval/acknowledgement must be received first and included in with the IRB/DSMC submission.

Deviations to protect subjects from immediate harm/danger should be reported immediately following the event to the entities outlined above.

Exceptions:

An exception is defined as a one-time, unintentional action or process that departs from the IRB and CTSRMC approved study protocol, intended for one occurrence. AND this action disrupts the study progress, such that the study design or outcome (endpoints) may be compromised, or the action compromises the safety and welfare of study subjects (i.e. requests to enroll and/or treat subjects outside of the current protocol criteria). Exceptions that meet this criteria will not be allowed unless reviewed and approved first by the Study Medical Monitor and the Study Principal Investigator, and then subsequently by the ACC DSMC, and IRB prior to this subject being enrolled/treated. Principal Investigator and Medical Monitor approval must be received first and included in with the IRB/DSMC submission. All entities should be given sufficient time to evaluate this request.

Examples of Exceptions/Deviations that require submission include:

- Violations of eligibility
- Dose adjustments/stopping rules that were not completed per protocol
- Other dosing errors

Events not deemed reportable as outlined above will require a PI assessment regarding study and/or safety impact.

9 Data Management

9.1 Analyses and Reporting

Data will be initially analyzed and reported on the 24 patients after the period of 12 months from starting lenalidomide maintenance. All subsequent data collected will be analyzed and reported in a follow-up clinical report.

9.2 Data Monitoring Committee

Interim analyses of toxicity are to be performed after the first three patients finish one month of lenalidomide maintenance therapy, and then quarterly thereafter.

This investigator initiated protocol is considered high risk as per the Abramson Cancer Center Data and Safety Monitoring Plan (DSMC). As such, high risk protocols are audited approximately three-six months from their first subject accrual and approximately every six month thereafter for the duration of the study by the ACC Department of Compliance and Monitoring (DOCM). However, this schedule may be changed at the discretion of the DSMC. High or quick enrolling studies may be audited more frequently as necessary.

The PI will be notified in advance of the selection of their protocol for review and cases are randomly selected. Three randomly selected subjects or 10% of the total accrual (up to 10 subjects), whichever is higher, are audited. A formal report is written to the PI within about 5 business days of the audit. The committee may alter the frequency of re-monitoring based on the audit findings and degree of deficiencies.

Upon review of inspection findings, the Committee designates the audit outcome as Minor, Moderate, or Major deficiencies. The deficiency assigned by the Committee initiates specific follow-up actions.

If an audit is unacceptable due to major deficiencies, representatives from the Department of Monitoring and Compliance (DOCM) meet with the PI to discuss the findings of the audit and review necessary corrective actions mandated by the DSMC. If the deficiencies involve subject safety or serious regulatory violations, the Cancer Center Director, DSMC Chair, and DSMC Administrative Director will meet to discuss necessary actions concerning study status.

The PI is given five business days to respond to these finding. An evaluation of the deficiencies will be re-evaluated upon receiving the PI's response. At this time, if the DSMC Chair and the Administrative Director do not find the response satisfactory, the IRB and OHR will be alerted of the actions taken by the ACC. The DSMC Director will update the IRB and OHR of the corrective actions being taken and progress being made.

Quarterly team meetings will also be held throughout the course of this study in order to discuss the protocol, ongoing patients, toxicity data, and applicable recruitment issues.

9.3 Study Auditing

9.3.1 Investigator Responsibilities

Investigator responsibilities are set out in the ICH guideline for Good Clinical Practice (GCP) and in the US Code of Federal Regulations.

The investigator will permit study-related monitoring, audits, and inspections by the IRB, ACC DOCM, the supporter (Celgene), government regulatory bodies, and University compliance and quality assurance groups of all study related documents (e.g. source documents, regulatory documents, data collection instruments, study data etc.). The investigator will ensure the capability for inspections of applicable study-related facilities (e.g. pharmacy, diagnostic laboratory, etc.).

The Investigator will permit study-related audits by Celgene or its representatives providing direct access to the facilities where the study took place, to source documents, to CRFs, and to all other study documents.

The Investigator, or a designated member of the Investigator's staff, must be available at some time during audits to review data and resolve any queries and to allow direct access to the subject's records (e.g., medical records, office charts, hospital charts, and study related charts) for source data verification. The data collection must be completed prior to each visit and be made available to the Celgene representative so that the accuracy and completeness may be checked.

Participation as an investigator in this study implies acceptance of potential inspection by government regulatory authorities and applicable University compliance and quality assurance offices.

10 Statistical Considerations

10.1 Design

This is a single arm phase I/II trial of lenalidomide maintenance for patients with high risk relapsed/refractory lymphomas who underwent high dose chemotherapy and ASCT. At 28-100 days post-ASCT, eligible patients will begin lenalidomide maintenance. The trial will be conducted in two stages. Phase I will evaluate the safety of lenalidomide implemented after ASCT by a 3+3 cohort design. Once the safety of a specific dose after ASCT is established, additional patients will be enrolled in phase II to evaluate the progression-free survival. PFS is a relevant endpoint for lenalidomide maintenance since it is expected to delay progression of disease post-ASCT. A monitoring rule for unacceptable toxicity due to lenalidomide will be followed during phase II.

10.2 Objectives

The primary objective:

-Dose-limiting toxicity due to lenalidomide

The secondary objective is to determine:

-Progression-free survival

-Overall survival

10.3 Endpoints

Dose-limiting toxicity (DLT) is defined as any grade 3 toxicity or higher that occurs during the first 28 days of therapy and is possibly, probably or definitely related to lenalidomide maintenance. Because certain levels of toxicity are considered acceptable in lymphoma therapy, the definition of DLT is limited to the following:

-Any grade 3 or higher non-hematologic toxicity possibly, probably or definitely related to lenalidomide.

-Grade 4 hematologic toxicity not attributable to progressive disease and that does not decrease to a grade 3 or less within 7 days of drug cessation.

-Lymphopenia of any grade and anemia of any grade are not considered a DLT.

-Nausea and vomiting are not considered DLTs unless they cannot be controlled with standard antiemetic therapy.

-Diarrhea is not considered a DLT unless it cannot be controlled with standard anti-diarrheal therapy.

-Nausea, vomiting, heartburn, anorexia, diarrhea, or constipation that improved to grade 1 or better within 2 days with the addition of symptom directed treatment will not be considered a DLT.

NCI Common toxicity criteria (CTC Version 4.0) grades will be employed. Toxicity unrelated to lenalidomide (i.e. clearly related to ASCT) will be scored separately.

Progression-free survival (PFS) is defined from date of ASCT (day 0) to first documented progression of disease, death due to any cause or last patient contact. Progression-free survival rate at 12 months (PFS12) is also of interest and is defined as the percentage of patients that are alive and progression-free at 12 months. Overall survival (OS) is defined as days from date of ASCT to death due to any cause or last patient contact.

Patients are enrolled 28 to 100 days after ASCT (day 0). Patients who complete one full cycle of lenalidomide maintenance or who experience DLT during the first cycle will be considered evaluable for DLT determination. Patients who withdraw from the study prior to initiation of lenalidomide maintenance, or who initiate and discontinue lenalidomide maintenance before completing one full cycle and do not experience DLT, remain in the study population and are followed for PFS and OS but do not contribute to the determination of DLT. These patients will be included in the estimation of PFS and OS, according to an intent-to-treat analysis plan. A secondary analysis of PFS and OS will include only patients who complete at least one full cycle of lenalidomide or who experience DLT at any point during cycle 1 (“evaluable population”). Patients who did not progress will be censored at the time of last contact. Evaluable patients contribute to determination of DLT, PFS and OS. Evaluable patient outcomes will be compared to historical rates for PFS12.

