⁴ Progression will be determined by the treating physician as based on clinical picture and radiographic findings. The initial imaging will be performed after ASCT, but prior to initiating maintenance lenalidomide therapy. During the maintenance phase, imaging (PET/CT or CT scan) will be performed every 3 months during the first year and every 4 months during the second year of maintenance. Imaging studies after the second year of maintenance will be at discretion of treating physician. During the first cycle of maintenance therapy, there will be two visits with physical exam. Then, participants will be seen on day 1 of each subsequent cycle. It will not be required to document progression by tissue biopsy (it will be at discretion of treating physician).

⁵ An additional safety assessment will be done 28 days (+/- 7 days) following the last dose of protocol therapy.

⁶ If screening assessments were done within 7 days of Day 1, they do not need to be repeated at Study Day 1.

⁷ Lenalidomide must be prescribed through and in compliance with Celgene's Revlimid REMS® program. Prescriptions must be filled within 14 days, unless the patient is a female of childbearing potential, in which case the prescription must be filled within 7 days. Consideration should be given to prescribing lenalidomide 5 to 7 days in advance of Day 1 of each cycle to allow time for required patient and prescriber surveys, and drug shipment to patient. Any unused Revlimid® (lenalidomide) should be returned to the patient for disposition in accordance with the Revlimid REMS® program.

⁸ Subjects will be followed every 3 months for the first 3 years after discontinuation of protocol therapy, and then annually thereafter; those patients who did not achieve hematological recovery by Day 100 after ASCT and never started on lenalidomide maintenance will also be followed every 3 months for the first year and then annually for anti-cancer treatment and progression/survival information.

3 Background and Rationale

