5.2.1 Inclusion Criteria

Subjects must meet the following inclusion/exclusion criteria to be registered to this study.

Inclusion criteria:

1. Able to understand and voluntarily sign the informed consent form.
2. Aged ≥ 18 years at the time of signing the informed consent form.
3. Able to adhere to the study visit schedule and other protocol requirements.
4. Biopsy-proven diagnosis of lymphoma (including diffuse large B-cell, mantle cell, follicular, marginal zone, peripheral T cell, small lymphocytic lymphoma with large cell transformation, and Hodgkin lymphomas).
5. Completion of at least 2 cycles of salvage chemotherapy, with pre-ASCT PET/CT imaging showing PET positive residual lesion(s) ($SUV > 2.5$).
6. Disease free of other malignancies for ≥ 2 years with exception of basal cell and squamous cell carcinomas of the skin, or carcinoma *in situ* of the cervix or breast.
7. Completion of high-dose chemotherapy with ASCT.
8. Hematologic recovery at 28-100 days after ASCT (defined as $ANC \geq 1,000$ and platelet count $\geq 60,000$).
9. All study participants must be registered into the mandatory Revlimid REMS® program and be willing and able to comply with the requirements of the Revlimid REMS® program
10. ECOG performance status of ≤ 2 at study entry (see Appendix B).
11. Patients undergoing planned consolidative radiation therapy must be finished with the therapy by day 100 after ASCT.
12. Laboratory test results within these ranges:
 - Absolute neutrophil count (ANC) $> 1,000/uL$
 - Platelet count $> 60,000/uL$
 - Serum creatinine ≤ 2.0 mg/dL
 - Total bilirubin $\leq 1.5 \times ULN$. Patients with known Gilbert's disease (as confirmed by study doctor) may participate with elevated bilirubin (serum bilirubin $\leq 2.0 \times ULN$) as long as their AST and ALT are within normal range.
 - AST (SGOT) and ALT (SGPT) $\leq 3 \times ULN$.

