13. Females of childbearing potential (FCBP)[†] must have a negative serum or urine pregnancy test with a sensitivity of at least 50 mIU/mL within 10 – 14 days and again within 24 hours prior to prescribing lenalidomide for Cycle 1 (prescriptions must be filled within 7 days) and must either commit to continued abstinence from heterosexual intercourse or begin TWO acceptable methods of birth control, one highly effective method and one additional effective method AT THE SAME TIME, at least 28 days before she starts taking lenalidomide. FCBP must also agree to ongoing pregnancy testing. Men must agree to use a latex condom during sexual contact with a FCBP even if they have had a successful vasectomy. See Appendix: Risks of Fetal Exposure, Pregnancy Testing Guidelines and Acceptable Birth Control Methods.
14. Able to take aspirin (81 or 325 mg) daily as prophylactic anticoagulation (warfarin or low molecular weight heparin may be used for patients intolerant of aspirin or at the discretion of the treating physician).

5.2.2 Exclusion criteria:

1. A PET/CT or CT scan post-ASCT which shows disease progression.
2. Any serious medical condition, laboratory abnormality, or psychiatric illness that would prevent the subject from signing the informed consent form.
3. Pregnant or breast feeding females (lactating females must agree not to breast feed while taking lenalidomide).
4. Any condition, including the presence of laboratory abnormalities, which places the subject at unacceptable risk if he/she were to participate in the study or confounds the ability to interpret data from the study.
5. Use of any other experimental drug or therapy within 28 days of initiating treatment with lenalidomide.
6. Known hypersensitivity to thalidomide.
7. The development of erythema nodosum, a blistering or desquamating rash, while taking thalidomide or similar drugs.
8. Any prior use of lenalidomide.
9. Concurrent use of other anti-cancer agents or therapies during study treatment.
10. Known seropositive for or active viral infection with human immunodeficiency virus (HIV) or hepatitis B virus (HBV). Patients who are seropositive because of hepatitis B virus vaccine are eligible.

[†] A female of childbearing potential is a sexually mature female who: 1) has not undergone a hysterectomy or bilateral oophorectomy; or 2) has not been naturally postmenopausal for at least 24 consecutive months (i.e., has had menses at any time in the preceding 24 consecutive months).

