5.3.5 Radiographic Evaluations

Subjects will undergo radiographic evaluations to assess disease status at the timepoints listed below. Timing of radiographic evaluations may be altered based on clinical indication or the discretion of the treating physician.

- PET/CT after at least 2 cycles of salvage chemotherapy, but prior ASCT (using separate PET scan and dedicated CT scan performed within one week is acceptable)
- Imaging (PET/CT or CT scan) after ASCT, but prior Cycle 1 of lenalidomide therapy
- Imaging (PET/CT or CT scan) every 3 cycles during the first year of lenalidomide maintenance therapy (near end of Cycles 3, 6, 9, 12)
- Imaging (PET/CT or CT scan) every 4 cycles during second year of lenalidomide maintenance therapy (near end of Cycles 16, 20, 24)

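### PFS and OS are counted from ASCT in patients who must be progression-free at days 28-100, and the historical controls have no matching landmark: the historical comparisons favour lenalidomide, and the 10% null is not justified for patients selected at entry

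*Combined protocol and SAP*

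**What the plan says.** Section 10.3 sets the time origin: "Progression-free survival (PFS) is defined from date of ASCT (day 0) to first documented progression of disease". OS also runs from ASCT, and PFS12 is the percentage alive and progression-free at 12 months.

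Entry comes later. Section 10.3: "Patients are enrolled 28 to 100 days after ASCT (day 0". Section 5.2.1 requires "Hematologic recovery at 28-100 days after ASCT", and Section 5.2.2 excludes "A PET/CT or CT scan post-ASCT which shows disease progression". Section 5.3.5 schedules the scan: "Imaging (PET/CT or CT scan) after ASCT, but prior Cycle 1 of lenalidomide therapy".

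The evaluable set is narrower. Under Section 10.3 a patient must complete one full cycle or have a DLT during it. That set is the one tested: "Evaluable patient outcomes will be compared to historical rates for PFS12". Section 10.6 declares evidence of success if more than 4 of 24 evaluable patients are alive and progression-free at 12 months. It gives a false-positive rate of 0.09 at a true rate of 10% and a false-negative rate of 0.11 at 30%.

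The controls appear in Sections 3.1 and 3.3: PET-positive patients with a median PFS of 5 months and 7% without progression at 12 months after ASCT. Section 10.7 rests the 10% null on a historical PFS12 below 10%. Section 4.1.2 plans to compare both PFS and OS with these controls. Nowhere is a landmark, delayed entry or restriction of the controls described.

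**The concern.** No enrolled patient can have died before entry, and none should have progressed on the post-ASCT scan. Those 28-100 days still count as PFS and OS time. Historical patients who progressed or died in the same interval stay in the control figures. The trial group would therefore look better than the controls even if lenalidomide did nothing.

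Two uses of the data are affected. One is the direct comparison of PFS and OS with the historical series. The other is the >4/24 rule, whose null is taken from an unselected historical rate. PFS is a secondary endpoint, but this rule decides whether the regimen is called worthy of further development (Sections 10.6 and 10.7).

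**Working it through.** **The plan's own figures.** With X binomial, n = 24: P(X > 4 | 0.10) = 0.085, stated as 0.09. P(X ≤ 4 | 0.30) = 0.111, stated as 0.11. Power is 0.889, stated as 89%. The arithmetic is right at 10%.

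**Inputs.** From Section 3.1: S(5 months) = 0.50 and S(12 months) = 0.07. From Section 10.3: entry at days 28-100. The documents give neither historical PFS at days 28-100 nor the distribution of entry times, so both are assumed. One month is 30.4375 days.
- Weibull through both points: shape 1.536, scale 6.35 months.
- Constant hazard in two pieces: ln 2/5 per month to month 5, then ln(0.50/0.07)/7 per month.

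**Formula.** The PFS12 expected with no drug effect, in patients progression-free at day d, is 0.07/S(d). Alpha is P(X > 4) at that rate.

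| Progression-free at | S(d), Weibull / constant | 0.07/S(d) | Alpha of >4/24 |
|---|---|---|---|
| Day 28 | 0.950 / 0.880 | 0.074 / 0.080 | 0.028 / 0.038 |
| Day 64 | 0.833 / 0.747 | 0.084 / 0.094 | 0.046 / 0.068 |
| Day 100 | 0.695 / 0.634 | 0.101 / 0.110 | 0.087 / 0.118 |
| Day 128 (day 100 plus one cycle) | 0.588 / 0.558 | 0.119 / 0.125 | 0.149 / 0.175 |

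**Uniform entry over days 28-100.** Averaging 0.07/S(d) gives 0.0851 (Weibull) or 0.0941 (constant hazard). Against 0.07 these are ratios of 1.22 and 1.34, and alpha is 0.048 or 0.069. Setting the average of S(t)/S(d) to 0.5 gives a median PFS from ASCT of 5.88 or 6.05 months, against 5.0.

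**Evaluable set.** Requiring patients also to be progression-free 28 days after entry gives mean rates of 0.0976 and 0.1069, with alpha 0.078 and 0.106. This is an upper bound. Patients with a DLT count without completing the cycle, and the first on-treatment scans are scheduled "near end of Cycles 3, 6, 9, 12", so little progression would be detected within cycle 1.

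**Break-even.** P(X > 4) = 0.10 at p = 0.105. From 7%, the rule stays within 0.10 if at least 0.07/0.105 = 67% of comparable historical patients were progression-free at the landmark. Under uniform entry the effective fraction is 0.07/0.0851 = 82% or 0.07/0.0941 = 74%. With the cycle-1 bound it is 72% or 65%.

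**Bound without a curve.** Day 128 is 4.2 months, before the 5-month median, so S(d) lies between 0.5 and 1. The rate then lies between 7% and 14%, and alpha between 0.023 and 0.24.

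**Other unselected baselines.** With uniform entry, alpha passes 0.10 once the unselected historical rate exceeds 8.5% (Weibull) or 7.8% (constant hazard). With the cycle-1 bound the limits are 7.5% and 6.9%.

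**The case against.** The strongest reply is that the null already sits 3 points above the only observed rate. From 7% with uniform entry, alpha is below the stated 0.09 on both curves. With the cycle-1 bound, only one curve passes 0.10, by 0.006. Screening is tied to count recovery, so day 100 is a limit rather than a typical entry day. This stands. A reader might infer that the 10% null is too low, or that 0.09 is wrong and the rule invalid. The documents do not support that. They also give a basis for 10%, a historical rate below 10%. What they lack is a reason why that rate applies to patients already progression-free at entry. The margin over 7% may absorb the selection, but no section says it was chosen for that purpose.

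It can also be said that the historical comparison is loosely specified, with no test against controls in Section 10.6, and that a bias of 1.5-2.4 percentage points is small beside the contrast of 7% with 30%. Both are true and limit the severity. They do not remove the bias, and the comparison of medians has no protective margin.

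Two defences do not hold. The intent-to-treat set in Section 10.3 is also enrolled at days 28-100. Footnote 8 of Section 2 says "those patients who did not achieve hematological recovery by Day 100 after ASCT and never started on lenalidomide maintenance will also be followed", but patients who never start treatment are outside the >4/24 rule. A confidence interval covers sampling error, not selection.

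**Conclusion.** The concern holds in a limited form. The direction is certain from the text: if followed as written, the PFS and OS comparisons with the historical controls favour lenalidomide. The size rests on assumed curves and uniform entry: PFS12 of about 8.5-9.4% against 7%, and a median of about 5.9-6.1 months against 5.0. No historical OS figure is given, so the OS bias cannot be sized. Any further selection through count recovery is not modelled.

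For the >4/24 rule, the 10% null is unjustified for patients selected at entry and nothing more. Alpha from 7% is about 0.05-0.07, or 0.08-0.11 with the cycle-1 upper bound, and exceeds 0.10 only if the entrants' no-effect rate is above about 10.5%. The day-100-plus-cycle figures (0.15-0.17) and the 14% bound are extremes, not expectations. This should be fixed, but it does not overturn the design.

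**What to change.** 1. For the historical PFS and OS comparisons (Sections 4.1.2 and 10.6), restrict both groups to patients alive and progression-free at a common landmark within days 28-100. Alternatively, use Kaplan-Meier with delayed entry at registration for trial patients, set against controls conditioned on being event-free at the same earliest entry day. A delayed-entry curve is itself conditional on that day, so the controls must match it. Do not compare with the unselected 7% or 5-month figures.

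2. In Sections 10.6 and 10.7, recompute the control PFS12 at the matching landmark from the institution's own PET-positive series, with count recovery where recorded. Allow for cycle 1 if the rule stays on evaluable patients. Report the rate with a confidence interval and state the alpha of >4/24 across it. The size of the series is not given. For illustration, 3/30 has an exact 95% interval of 2-27% and 10/100 one of 5-18%, so a point estimate alone cannot separate 10% from 11-13%.

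3. Keep 10% and >4/24, with the justification written in, unless the landmark rate is clearly above about 10.5%. In that case restate null, cut-off, alpha and power at n = 24. For example, at nulls of 11-13%, >4/24 has alpha 0.12-0.19, while >5/24 has alpha 0.04-0.08 with power at 30% falling from 0.89 to 0.77.

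The cost is a re-analysis of existing data, some SAP wording, and possibly a less favourable stated alpha or power. No new patients or visits are needed.

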Grade 4	
 • If Grade 4, discontinue lenalidomide. Remove patient from study.
Desquamating (blistering) rash- any Grade	
 • Discontinue lenalidomide. Remove patient from study.
Lenalidomide-related neuropathy	
 • If Grade 3, hold (interrupt) lenalidomide dose. Follow at least weekly. • If the toxicity resolves to ≤ grade 1 prior to Day 28 of the current cycle, restart lenalidomide at next lower dose level and continue through the scheduled Day 28 of the current cycle. Otherwise, omit for remainder of cycle and reduce the dose of lenalidomide by 1 dose level at the start of the next cycle. Omitted doses are not made up.
Grade 3	
Grade 4	
 • If Grade 4, discontinue lenalidomide. Remove patient from study.
Venous thrombosis/embolism ≥ Grade 3	
 • Hold (interrupt) lenalidomide and start therapeutic anticoagulation, if appropriate. • Restart lenalidomide at investigator's discretion (maintain dose level). • See Anticoagulation Consideration (Section 5.6.1.2)
Hyperthyroidism or hypothyroidism	
 • Omit lenalidomide for remainder of cycle, evaluate etiology, and initiate appropriate therapy. • See Instructions for Initiation of a New Cycle and reduce the dose of lenalidomide by 1 dose level.

Table 2: Dose Modifications :	
NCI CTC Toxicity Grade	Dose Modification Instructions (also see Instructions for Initiation of a New Cycle above)
Creatinine \geq Grade 2 ($>1.5 - 3.0 \times$ baseline)	
 • Hold lenalidomide dose until resolved to grade < 2. When re-starting, reduce lenalidomide by 1 dose level. Omitted doses are not made up.
Other non-hematologic toxicity \geq Grade 3	
 • Hold (interrupt) lenalidomide dose. Follow at least weekly. • If the toxicity resolves to \leq grade 2 prior to Day 28 of the current cycle, restart lenalidomide and continue through the scheduled Day 28 of the current cycle. Otherwise, omit for remainder of cycle. Omitted doses are not made up. For toxicity attributed to lenalidomide, reduce the lenalidomide dose by 1 dose level when restarting lenalidomide.

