5.7 Discontinuation of Study Treatment

Study treatment will continue until the completion of 24 cycles of lenalidomide maintenance therapy, or the occurrence of any of the following events:

- Disease progression (See Appendix D)
- Adverse event(s) that, in the judgment of the Investigator, may cause severe or permanent harm or which rule out continuation of the treatment regimen.
- Discontinuation or interruption in lenalidomide therapy for ≥ 28 consecutive days.
- Withdrawal of consent
- Lost to follow up
- Death
- Pregnancy or a positive pregnancy test

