10.4 Phase I Design

A 3+3 design will be employed to determine the tolerability of lenalidomide maintenance at the dose of 10 mg daily in this setting. The dose will not be escalated, but in the event of 2 or more DLTs at 10 mg, the dose will be de-escalated to 5 mg.

Dose Level 1: Three evaluable patients will be treated at 10 mg lenalidomide.

If 2 or more of 3 evaluable patients have DLT, then the dose will be de-escalated to 5 mg.

If 0 or 1 of 3 evaluable patients has DLT, then 3 more evaluable patients will be treated at 10 mg daily.

If 0 or 1 of 6 evaluable patients has DLT, then 10 mg will be declared the appropriate dose for phase II part of the trial. 18 additional evaluable patients will then be enrolled in phase II.

If 2 or more of 6 evaluable patients have DLT, then the dose will be de-escalated to 5 mg daily.

Dose Level -1: Three evaluable patients will be treated at 5 mg lenalidomide.

If 2 or more of 3 evaluable patients have DLT, then the appropriate dose is not defined and the trial will be terminated.

If 0 or 1 of 3 evaluable patients has DLT, then 3 more evaluable patients will be treated at 5 mg daily.

If 0 or 1 of 6 evaluable patients has DLT, then 5 mg will be declared the appropriate dose.

18 additional evaluable patients will then be enrolled in phase II.

If 2 or more of 6 evaluable patients have DLT, then the appropriate dose is not defined and the trial will be terminated.

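### Does leaving cycle-1 stops for lenalidomide toxicity below DLT grade out of the 3+3 count make the dose decision unsound?

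*Combined protocol and SAP*

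**What the plan says.** Section 10.3 makes a patient evaluable for DLT by completing cycle 1 or by having a DLT in it. The rule on the others concerns patients "who initiate and discontinue lenalidomide maintenance before completing one full cycle and do not experience DLT, remain in the study population". They stay in the PFS and OS analyses, while the same sentence takes them out of the 3+3 count with the words "but do not contribute to the determination of DLT". The rule does not separate stops caused by the drug from other stops.

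Section 10.4 opens with "A 3+3 design will be employed to determine the tolerability of lenalidomide maintenance at the dose of 10 mg daily in this setting". It then states the criterion: "If 0 or 1 of 6 evaluable patients has DLT, then 10 mg will be declared the appropriate dose".

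A non-hematologic DLT is "Any grade 3 or higher non-hematologic toxicity possibly, probably or definitely related to lenalidomide" (section 10.3). Table 2 in section 5.5.3 lists "Desquamating (blistering) rash- any Grade" with the instruction "discontinue lenalidomide. Remove patient from study". Section 5.7 also ends treatment for "Adverse event(s) that, in the judgment of the Investigator, may cause severe or permanent harm or which rule out continuation of the treatment regimen", with no grade threshold.

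**The concern.** The primary objective is safety and the appropriate dose, and section 10.4 speaks of tolerability. A patient who has to give up the drug within 28 days because of the drug is evidence on tolerability, yet leaves both numerator and denominator of the figure that sets the dose. With 1 DLT in 6 evaluable patients (17%), 10 mg passes. If a seventh treated patient stopped for milder drug toxicity, 2 of 7 treated patients (29%) had a DLT or a toxicity stop. The dose then goes to 18 more evaluable patients, and no section plans that second fraction beside the 3+3 decision or the phase II looks. If such stops were frequent and unseen, a poorly tolerated dose could be carried forward.

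**Working it through.** **The plan's own figures.** Section 10.5 uses a beta(1,5) prior, so the posterior after x DLTs in n patients is Beta(1+x, 5+n−x). The upper tail at 0.33 is 0.836 for 7/12 (Beta(8,10)), 0.803 for 9/18 (Beta(10,14)) and 0.780 for 11/24 (Beta(12,18)). The plan states 0.84, 0.80 and 0.78, so the monitoring table reproduces.

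**Inputs for the check.** The documents give no rate of such stops. I assume w = 2%, 5% or 10% per treated patient, and a DLT probability d = 10%. The pass rule is from section 10.4. Because 0 or 1 DLT in 3 always leads to expansion, P(pass) = P(X ≤ 1 of 6).

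**Direction of the effect.** Among evaluable patients the DLT rate is d/(1−w). At w = 5% this is 0.10/0.95 = 0.105, and P(pass) = 0.8947^6 + 6 × 0.1053 × 0.8947^5 = 0.513 + 0.362 = 0.875. If stoppers stayed in the cohort as patients without DLT, P(pass) at d = 0.10 would be 0.886. Replacing them lowers the chance of passing slightly, because the replacement gives another chance to see a DLT.

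**Size.** The number of stops before the sixth evaluable patient is negative binomial and independent of the DLT count among evaluable patients. Hence P(pass with at least one stop) = P(pass) × [1 − (1−w)^6]. At w = 5% this is 0.875 × (1 − 0.735) = 0.232. More than 33% of treated patients are affected when a pass comes with 1 DLT and at least 2 stops (3/8 or more), or with 0 DLTs and at least 3 stops (3/9 or more).

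| Assumed w | P(pass) | Pass with ≥1 stop | Pass with DLTs + stops ≥2 | Pass with >33% of treated affected | Expected stops over 24 evaluable, 24w/(1−w) |
|---|---|---|---|---|---|
| 2% | 0.882 | 10% | 4.5% | 0.3% | 0.5 |
| 5% | 0.875 | 23% | 12% | 1.9% | 1.3 |
| 10% | 0.863 | 40% | 25% | 7.4% | 2.7 |

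The 33% in section 10.5 is a limit for DLTs only; it serves here as a yardstick. The 2/7 example (29%) lies below it. Its exact 95% interval, 3.7% to 71%, overlaps almost wholly with that of 1/6, 0.4% to 64%.

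**How such stops could arise.** Blistering rash of grade 1–2 is the only mandatory permanent stop below DLT grade, and exclusion 7 in section 5.2.2 bars patients who had such a rash on thalidomide or similar drugs. Most other entries in Table 2 lead to a hold or a reduction. The discretionary route in section 5.7 is worded for events with serious consequences; a related non-hematologic event of that kind will often be grade 3 or higher and so already a DLT. A 10% rate is hard to reconcile with this.

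**Where a stop would be seen.**
- Section 6.2: every adverse event from first dose is recorded, with relationship to the drug and the action taken.
- Section 6.3.2, DSMC: events below grade 3 also go to the committee if they may affect safety, are clinically significant, or may be related to the drug. A related stop fits that description.
- Section 6.3.2, medical monitor: all adverse events are reviewed by a person outside the trial, who may recommend suspension or termination.
- Section 9.2: toxicity is analysed after the first three patients complete one month and quarterly after that, with quarterly team meetings on toxicity.
- Section 10.6: all observed toxicities are graded and tabled, with no restriction to evaluable patients.

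**The case for a change.** The strongest reply is that none of these provisions names the combined count. Section 10.6 makes stratification by relatedness optional, and section 9.2 does not specify the content of the interim analyses. With six patients setting the dose, one or two stops would alter the impression of tolerability, and the extra line would use data already collected.

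The facts in that reply stand: the exclusion is as described, the route exists, and no section plans the count. They do not show that the plan goes wrong. Section 10.2 names dose-limiting toxicity as the primary objective, and section 10.4 makes tolerability operational through DLTs in evaluable patients, a common convention for a 3+3. In a single-institution cohort of about six, a related stop reported through these channels is unlikely to go unnoticed.

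Nor would the combined figure measure what is wanted. It leaves out holds and reductions. A patient held for the rest of cycle 1 for grade 3 thrombocytopenia and then reduced under Table 2 also did not take 10 mg for a full cycle, yet would not be counted. The figure could itself be misread as a tolerability rate.

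Two nearby wording points are clerical. The table row in section 10.5 refers to treated patients, but the text introducing the table says evaluable. Table 2 speaks of removal from study, but sections 5.8 and 10.3 already require follow-up after discontinuation.

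**Conclusion.** The concern does not hold. The evaluability rule is explicit, does not push the defined DLT rate toward safety, and leaves the decision rules sound as written. Toxicity stops below DLT grade are outside the 3+3 count but inside the safety data, the planned tables and the independent review. The sizes rest entirely on assumed rates: with a 10% DLT rate and stop rates of 2% to 10%, a pass with more than 33% of treated patients affected has probability 0.3% to 7.4%, and the narrow route makes the lower end more plausible. A descriptive combined count would alter no decision rule and would be an incomplete measure of tolerability. The authors may add it if they wish; its absence is not a deficiency.
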